- 3) Assessment of the incidence of biopsy proven chronic allograft nephropathy at 1, 3 and 5 years post-transplant compared to that reported in the SRTR database for similar patients.
- 4) Assessment of the composite of occurrence of malignancies, and opportunistic infections by 1, 3 and 5 years compared to that reported in the SRTR database for similar patients.
- 5) Long term assessment of donor-specific immune responsiveness after prolonged therapy with belatacept (with or without sirolimus), and during and following drug withdrawal as determined by in vitro alloresponsiveness in CFSE mixed lymphocyte reactivity and ICCS.
- 6) Characterization of the repopulating immune system with regard to cell surface phenotype using MFC compared to prior experience with alemtuzumab alone or combined with other related regimens and,
- 7) Comparison of the function and survival of allografts transplanted using this protocol to historical controls transplanted using conventional immunosuppression to establish an initial assessment of this approach in a general transplant population.

Clinical Therapy:

Alemtuzumab. At the time of transplantation patients will be given a single dose of methylprednisolone 500 mg intravenously over 30 minutes followed by acetaminophen 650 mg orally or rectally and diphenhydramine 50 mg intravenously, followed in one hour by alemtuzumab, 30mg, given intravenously over three hours.

Transplantation. Transplantation will be performed using standard surgical techniques for organ engraftment. Patients will be cared for perioperatively on the transplant unit. Technical aspects of the postoperative management will be according to the standard of care.

Belatacept. Belatacept will be given within 24 hours of transplantation via a peripheral intravenous catheter at a dose of 10mg/kg (actual body weight) infused over 30 mins. The dose will be repeated on study days 4 (post op day 3) and 8 (post op day 7), then every 2 weeks for 5 additional doses. Thereafter, belatacept will be given once every 4 weeks (+/- 3 days) at 10mg/kg through 6 months then at 5mg/kg indefinitely.

Sirolimus. Sirolimus will be started on postoperative day 1 at a dose of 2 mg per day orally. Doses will be adjusted to maintain 24-hour trough levels of 8-10ng/ml until the drug is weaned as described below.

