2.2 Secondary Objectives

1. Determination of the prognostic ability of assays based on surface phenotype changes seen during homeostatic repopulation, including Ki67 expression, T_{REG} and B_{TRANS} cell surface phenotypes, and T_M to T_{REG}/B_{TRANS} balance, with regard to the anticipation of successful immunosuppressive drug withdrawal.
2. Assessment of the proposed therapies to prevent biopsy proven acute rejection at 1, 3 and 5 years post-transplant compared to the standard reported in the SRTR database for similar patients;
3. Assessment of the incidence of biopsy proven chronic allograft nephropathy at 1, 3 and 5 years post-transplant compared to that reported in the SRTR database for similar patients;
4. Assessment of the composite of occurrence of malignancies, and opportunistic infections by 1, 3 and 5 years compared to that reported in the SRTR database for similar patients;
5. Long term assessment of donor-specific immune responsiveness after prolonged therapy with belatacept (with or without sirolimus), and during and following drug

- withdrawal as determined by in vitro alloresponsiveness in CFSE mixed lymphocyte reactivity and ICCS;
6. Characterization of the repopulating immune system with regard to cell surface phenotype using MFC compared to prior experience with alemtuzumab alone or combined with other related regimens; and,
 7. Comparison of the function and survival of allografts transplanted using this protocol to historical controls transplanted using conventional immunosuppression to establish an initial assessment of this approach in a general transplant population.

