3.3 Criteria for Evaluation

1. Number of patients successfully withdrawn from sirolimus for 12 months after last dose of sirolimus
2. Biopsy proven acute rejection or chronic allograft nephropathy by 1, 3 and 5 years
3. Evidence of donor-specific hyporesponsiveness by MLR and ICCS
4. Evidence of regulatory T cell and transitional B cell activity in the periphery and allograft
5. Donor specific and third party alloantibody formation

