3.4 Sample Size Determination

Our prior experience with alemtuzumab, belatacept and sirolimus, in recipients of live donor kidneys suggests that this regimen is very effective in preventing acute rejection, with only one steroid sensitive, clinical rejection episode seen in the first year. However, with the liberalization of the inclusion criteria, it is anticipated that an acute rejection rate prior to initiation of sirolimus withdrawal of up to 20% will exist, excluding up to four patients from eligibility for sirolimus withdrawal. It also is anticipated that four additional patients will either not meet other criteria for withdrawal or will refuse to be withdrawn from immunosuppression. The number of patients has therefore been chosen to have approximately 12 patients who are eligible for sirolimus withdrawal and in whom withdrawal is attempted, in order to establish a reasonable proof-of-concept. This target of 12 subjects in whom sirolimus withdrawal is attempted will allow for the detection approximately 6 subjects successfully withdrawn from sirolimus for one year, assuming the probability of a subject in whom withdrawal is attempted being successfully withdrawn from sirolimus for one year is 50%, a rate determined by the current cohort. Since there are no trials exploring monotherapy belatacept reported in the literature or registered with ClinicalTrials.gov, this cohort of patients withdrawn successfully will represent a significant finding.

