4.2 Analyses

Demographics and Baseline Characteristics

Demographic and baseline characteristics of patients will be summarized descriptively by treatment group, by means and standard deviations (SDs) for continuous variables and frequency distribution for categorical variables. Summaries will be performed based on the data set.

Efficacy Analyses

No formal statistical hypothesis testing will be performed for the primary endpoint. All efficacy analyses will generally be descriptive in nature. The primary efficacy analysis will be to assess the proportion of patients successfully withdrawn from sirolimus for one year. The point estimate of this proportion and the exact two-sided 95% confidence interval (CI) will be provided for each treatment group. A patient will be considered to be successfully withdrawn from immunosuppression for one year if the patient has been administered only belatacept for a period of 365 days, following successful completion of sirolimus, and has not experienced biopsy-proven acute rejection, formation of DSA, or graft loss for this same period of 365 days. Secondary efficacy outcome measures involving incidences and proportions will be descriptively summarized with point estimates and exact, two-sided 95% CIs by treatment group. Other secondary efficacy outcome measures will be descriptively summarized by means and SDs for continuous outcomes and frequency distributions for categorical outcomes.

Safety Analyses

All AEs and SAEs will be summarized by treatment group. Laboratory values will also be descriptively summarized.

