6.2 Maintenance Immunosuppressive Reduction

Beginning any time after year 1 (week 53), participants who are deemed eligible for sirolimus withdrawal as determined by clinical and flow cytometric parameters

(described below) may be withdrawn from sirolimus. Withdrawal will proceed at a maximum rate of 66% of the original dose for 4 weeks, 33% of the original dose for another 4 weeks, then discontinued. However, each reduction in dose will be predicated on stable flow cytometric profile.

Criteria for Sirolimus Withdrawal. Participants will be deemed eligible for withdrawal of sirolimus if they meet all of the following criteria:

1. No episodes of steroid resistant acute rejection since transplant, and no episodes of steroid sensitive rejection for 12 months.
2. Stable renal function, as defined by both of the following:
 - a. GFR, using calculated CrCl (Cockcroft-Gault) of > 40ml/min.
 - b. Creatinine, which in the 12 weeks preceding withdrawal has not increased more than 20% with respect to the lowest creatinine observed during the same period.
 - c. Absence of histologic evidence of acute or chronic rejection on pre-withdrawal renal biopsy according to the Banff criteria for acute, chronic and humoral rejection.
3. Absence of DSA reactivity, as measured by de novo anti-donor-HLA antibodies.
4. ALC at least 80% of the baseline ALC prior to alemtuzumab.
5. Ki67 expression on CD3+ T cells that is within 1 standard deviation of the normal expression in untreated controls. Ki67 is typically seen in <3% of lymphocytes in health controls and a value >5% exceeds the value accepted for purposes of this trial.

For determining eligibility, a renal biopsy will be obtained and creatinine clearance will be estimated. Requisite blood samples will be obtained within two weeks before starting sirolimus withdrawal. Results of laboratory assessments of immune status will be made available to, and reviewed by, the investigator. These data will be reviewed with the knowledge of previous results of immunosuppression withdrawal obtained in the current trial up to the time of review.

Maintenance Immunosuppressive Therapy

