| BK viremia/viruria PCR | | X | | | X |
| Adverse Events | X | X | | | X |
| QoL | | | | X | |
| Neurologic Exam | | | X | | |
| Immunogenicity | | | | X ^a | |

^a These are specific study related assays for reporting purposes.

Long-Term Follow-Up Cohort 1

| Tests / Evaluations | Every 6months | Yearly |
|----------------------------------------------------------------------|----------------------|----------------|
| Telephone Reporting | X | |
| Serum Chemistry/ lipids /CBC | X | |
| Sirolimus trough | | X |
| Lymphocyte subsets | X | |
| Peripheral transcription | | X |
| CMV and EBV PCR | X | |
| BK viremia/viruria PCR | X | |
| PRA | | X |
| Anti-Donor Antibody | | X |
| Donor-specific and third party mixed lymphocyte responsiveness/ ICCS | | X |
| Renal Biopsy | | X ^b |
| Intragraft mRNA Analysis | | X ^b |
| Adverse Events | X | X |
| QoL | X | |
| Neurologic Exam | X | |
| PK | | |
| Immunogenicity | X | |

=

^b To be performed prior to weaning patient to monotherapy (generally at 12 months) and again after stable on monotherapy as clinically indicated.

Long-Term Follow-Up Cohort 2

| Tests / Evaluations | Monthly after Year 1 | Every 3 months from 6 - 24Months | Every 6 months | Yearly |
|----------------------------------------------------------------------|-----------------------------|-----------------------------------------|-----------------------|----------------|
| Telephone Reporting | | | X | |
| Serum Chemistry/ lipids /CBC | X ^c | | X | |
| Sirolimus trough ^d | X | | | X |
| Lymphocyte subsets Ki67 | | | X | |
| Peripheral transcription | | | | X |
| CMV and EBV PCR | | X | X | |
| BK viremia/viruria PCR | | X | X | |
| PRA | | | | X |
| Anti-Donor Antibody | | | | X |
| Donor-specific and third party mixed lymphocyte responsiveness/ ICCS | | | | X |
| Renal Biopsy | | | | X ^b |
| Intra-graft mRNA Analysis | | | | X ^b |
| Adverse Events | X ^e | | | |
| QoL | | | X | |
| Neurologic Exam | | | X | |
| Immunogenicity | | | X | |

^cStudy participants may have these labs drawn more or less frequently as deemed clinical necessary by the investigator.

^dStudy participants who are not weaning sirolimus and are on a stable, low dose can have trough levels monitored as frequently as a monthly basis or as clinically indicated.

^eIf study participant is on a stable dose of sirolimus, not weaning, and receiving commercial belatacept as an outpatient, then adverse events may be assessed every three months.

Year 1 Medication Flowchart

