known to arise in transplanted kidneys that could confound the interpretation of the study.¹³³⁻¹³⁴ In the event that subclinical rejection is detected, the patient will receive anti-rejection therapy in keeping with the standard of care, generally an oral steroid taper over 30 days and reevaluation of the patient's need for chronic immunosuppression. A follow-up biopsy will be performed in 3 months to assess resolution of subclinical rejection. Subclinical rejection, once resolved, will not in and of itself remove the patient from consideration of weaning, if it occurs during a period of homeostatic repopulation.

Renal biopsies also will be performed if any sustained rise in serum creatinine of greater than or equal to 30% of the baseline creatinine is detected. Baseline creatinine will be defined as the mean of five stable serum creatinine values within the first three months post-transplant. Stable is defined as a variance of +/- 20% or less of any value. Clinical suspicion of allograft pathology based on other grounds (urine cytology, pyuria, proteinuria, etc.) also will be considered grounds for biopsy at the discretion of the attending physician. An attending transplant physician or surgeon will perform all biopsies. The risks of transplant kidney biopsy will be included in the informed consent process for the protocol. At the time of each biopsy (protocol or clinically indicated), blood will be drawn for peripheral phenotyping and lymphocyte harvest (50ml heparinized).

Patients will be evaluated for cellular alloreactivity, donor-specific hyporesponsiveness and viral specific responsiveness pre-operatively, at the time that sirolimus withdrawal commences, 3 months after sirolimus withdrawal, at the time of clinical rejections, and at study termination. This will require 50ml of heparinized blood to be drawn at these time points and cryopreserved for analysis.

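### Donor-specific MLR/ICCS at the two withdrawal-anchored time points comes from a selected group (about 12 of 20), and section 4.2 specifies no within-patient change, so comparing means can show a change when no patient changed

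*Combined protocol and SAP*

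**What the plan says.** Secondary objective 5 (synopsis and 2.2) is "Long term assessment of donor-specific immune responsiveness after prolonged therapy with belatacept (with or without sirolimus), and during and following drug withdrawal", measured by CFSE mixed lymphocyte reactivity and ICCS. Section 3.3 lists "Evidence of donor-specific hyporesponsiveness by MLR and ICCS" as an evaluation criterion and gives no cut-off.

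Section 9.2 schedules the assay pre-operatively and then "at the time that sirolimus withdrawal commences, 3 months after sirolimus withdrawal, at the time of clinical rejections, and at study termination". The tables in 8.1 add a 6-month assay and, in long-term follow-up, a yearly "Donor-specific and third party mixed lymphocyte responsiveness/ ICCS". Neither of these depends on withdrawal.

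Entry to withdrawal is governed by 6.2. Its first criterion is "No episodes of steroid resistant acute rejection since transplant, and no episodes of steroid sensitive rejection for 12 months". The others are stable renal function, a pre-withdrawal biopsy free of rejection, no DSA, and ALC and Ki67 thresholds. Section 3.1 makes withdrawal subject to the patient's consent. Section 3.4 plans for "approximately 12 patients who are eligible for sirolimus withdrawal and in whom withdrawal is attempted".

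On analysis, 4.2 states: "Other secondary efficacy outcome measures will be descriptively summarized by means and SDs for continuous outcomes and frequency distributions for categorical outcomes". Section 4.1 plans subgroup analyses by withdrawal attempted or not attempted, for selected endpoints that it does not name. Appendix B intends to quantify changes in alloreactive T cells over time but gives no statistical method.

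**The concern.** Objective 5 is a question about change. The two samples that address the withdrawal period most directly can be taken only from patients who enter withdrawal. Several of the entry criteria (rejection history, biopsy, DSA) reflect the alloimmune process that the assay is meant to measure.

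If the later means are set beside the pre-transplant mean of everyone, the comparison mixes two things: change within patients, and a change in which patients are counted. A lower mean could then be read as donor-specific hyporesponsiveness, a listed evaluation criterion, when it partly describes who was eligible. A third-party control would not remove this if rejecters differ mainly in donor reactivity, because leaving them out would lower the donor mean more than the third-party mean.

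**Working it through.** **Inputs.** Enrolled in the new cohort: 20 (3.1). Lost to acute rejection before withdrawal: up to 20% (3.4). Lost to other criteria or refusal: 4 (3.4). Success probability once withdrawal is attempted: 50% (3.4). The documents give no MLR/ICCS level, SD, or link between the assay and eligibility, so d below is an assumption.

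**The plan's own figures.** 0.20 × 20 = 4; 20 − 4 − 4 = 12 attempted; 12 × 0.50 = 6 successes. Both figures in 3.4 reproduce. Eight of 20 (40%) are absent from the withdrawal-anchored samples, and up to four of those eight because of rejection.

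**Apparent change when no patient changes.** Hold every patient's value constant:

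mean of all 20 − mean of the 12 = (8/20) × (mean of the absent 8 − mean of the present 12)

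- Only the four rejecters are higher, by d: the absent eight average d/2 higher, so the fall is 0.40 × d/2 = 0.20d.
- All eight absent patients are higher by d: the fall is 0.40d.
- Eligibility unrelated to the assay: d = 0 and the fall is zero.

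For an assumed d of 0.5 to 1 between-patient SD, the fall is 0.10 to 0.20 SD in the first case and 0.20 to 0.40 SD in the second.

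**Illustration (assumed values, arbitrary units).** Four rejecters read 40 and the other 16 read 20. The mean of 20 is (4 × 40 + 16 × 20)/20 = 24.0 and the mean of the 12 is 20.0, an apparent fall of 4.0, or 17%.

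**Sensitivity to re-entry.** Section 6.2 does not bar a patient whose steroid-sensitive rejection was more than 12 months earlier. If k of the four rejecters later enter withdrawal, the later mean is (12 × 20 + 40k)/(12 + k):

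| k | n | later mean | apparent fall |
|---|---|---|---|
| 0 | 12 | 20.0 | 4.0 |
| 1 | 13 | 21.5 | 2.5 |
| 2 | 14 | 22.9 | 1.1 |
| 4 | 16 | 25.0 | −1.0 (a rise) |

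**Paired alternative.** In the same 12 patients at both times, the change is exactly 0 when no patient changes.

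**Precision.** Take unit SD and an assumed within-patient correlation of 0.7. The SE of the paired change is √(2 × 0.3/12) = 0.22. The SE of the difference between the mean of 12 and the mean of 20, allowing for the 12 shared patients, is √(1/12 + 1/20 − 2 × 0.7/20) = 0.25. The formula √(1/12 + 1/20) = 0.37 ignores the overlap. The gain from pairing is therefore mainly freedom from selection, with little gain in precision.

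**The case against.** The best defence has four parts.

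- **The plan does not prescribe the faulty comparison.** Section 4.2 does not say that means will be shown at each time point or that 20 will be compared with 12. The summarised outcome could be change from baseline, in line with the intent in Appendix B, and the 3.3 criterion could be read as categorical. This stands as a limit on the wording. It does not close the gap, because nothing specifies paired change, and a proportion hyporesponsive would have the same shifting denominator.
- **Other samples are not tied to withdrawal.** The 6-month, yearly and termination assays include patients who never withdraw. This stands, and it confines the point to two time points. Those assays do not replace the samples at the start of withdrawal and 3 months after it. Later samples from steroid-resistant rejecters are also not assured: 6.6 takes these patients off study treatment, and 6.4 specifies only 8 weeks of safety follow-up after that.
- **The 4.1 subgroups help.** Applied to MLR/ICCS, they would allow the attempted group to be viewed at baseline and at the start of withdrawal. This stands in part: the endpoints are unnamed and no paired change is specified.
- **The analysis is descriptive, in a small mechanistic study.** No test or decision rule depends on it. That limits the consequence, but a descriptive mean can still be read as change.

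A reader might also infer that the withdrawal samples come only from patients who never had rejection or DSA. The documents do not support that. Section 6.2 admits patients with an older steroid-sensitive rejection, 6.6 lets patients continue after an early one, and 9.2 does not let resolved subclinical rejection by itself bar weaning if it occurs during homeostatic repopulation. Section 9.2 also does not make the 3-month sample conditional on absence of rejection or DSA.

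**Conclusion.** The point holds for the two withdrawal-anchored samples. With no patient changing, comparing the all-patient pre-transplant mean with the later mean gives an apparent fall of 0.20d if only the up to four rejecters differ, 0.40d if all eight absent patients do, and zero if eligibility is unrelated to the assay. The 20, the four and the 12 are the plan's; d is assumed.

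Two stronger readings are tempting and should not be drawn. The first is that the bias is shown to favour the regimen. That direction is likely, but the documents give no link between pre-transplant reactivity and eligibility, and re-entry of rejecters can shrink or reverse the effect. The second is a fall of 0.70d, obtained as (14/20)d by counting only the six expected successes. Those are successes at one year, whereas the affected sample is at 3 months, when up to about 12 patients could contribute. That figure also gives all 14 other patients, refusers included, the same excess reactivity.

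**What to change.** Add to 4.2, for donor-specific and third-party MLR/ICCS:

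> At the start of sirolimus withdrawal and 3 months after it, the paired change from the pre-transplant value will be reported in patients with both samples, with a 95% CI and the number of patients at each time point. This change describes patients who entered withdrawal. Pre-transplant values will be shown by withdrawal status (not attempted, attempted and failed, successful). Samples triggered by rejection will be reported separately and not pooled with scheduled samples.

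In 4.1, name MLR/ICCS among the endpoints for the attempted/not-attempted subgroups.

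The cost is SAP wording and a small amount of extra analysis, since the samples are already scheduled. The paired summaries rest on fewer patients (at most about 12) than the baseline mean. They remove the artefact of changing membership, but they still describe only patients who entered withdrawal, which is why the text should say so.

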3 STUDY DESIGN AND EVALUATION

3.1 Study Design

This will be a single-center, open-label, non-randomized, proof-of-concept study in recipients of living or deceased donor renal transplants (DDRTs). Twenty renal transplant patients will be enrolled, at least 10 of which will be recipients of DDRTs. At the time of transplantation, participants will be given alemtuzumab, 30mg intravenously over three hours. Participants will receive combination maintenance therapy with sirolimus and belatacept for at least one year. Patients' absolute lymphocyte counts (ALCs) and percent expression T cell of Ki67 will be assessed monthly. After one year of therapy, participants may consent to and begin sirolimus withdrawal or continue therapy through study close. Patients wishing to withdraw from sirolimus will begin sirolimus weaning when their ALC has reached at least 80% of baseline and had two consecutive monthly assessments of their percent expression of Ki67 fall within at least one standard deviation of the Ki67 expression of a healthy control population. Weaning will be triggered of the Ki67 expression, with other surface phenotype assessments being followed observationally. Patients meeting these parameters will be weaned off of sirolimus by halving the dose and/or increasing the dosing interval over at least a three-month period. Each dose reduction will require stable (within 1 standard deviation) peripheral Ki67 expression. After sirolimus is discontinued, patients will remain on belatacept monotherapy indefinitely. Clinical and mechanistic observation will continue for the duration of the study to assess the efficacy and safety of this approach. Subjects will be followed for at least five years.

Duration of Study

Subjects will be followed for at least five years. Belatacept is now approved by the FDA. Therefore, subjects remaining on belatacept at the conclusion of their five-year participation would be eligible to continue this therapy. If at the conclusion of this study belatacept is not commercially available to patients, the Principal Investigator will discuss other treatment options utilizing approved immunosuppressive therapies with the subject. If subjects are successfully weaned from sirolimus as a result of their participation in this protocol, there will be no need for consideration of alternative therapy.

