4 STATISTICAL METHODOLOGY

4.1 Data Set Descriptions

A summary of all patient data will be kept in a study database developed for this study. In addition to the experimental data, this database will include recipient and donor demographics and transplant relevant medical history (comorbidities, HLA type, etc.), graft function, immunosuppressive medications and levels, and a running summary of the patient's post transplant course. Data will be recorded and reported in accordance with the standards required by the United Network for Organ Sharing (UNOS). The data set will consist of all patients who are randomized and transplanted and will be used for all

efficacy analyses. The as-treated data set will consist of all patients who receive at least one dose of belatacept and will be used for all safety analyses. Subgroup analyses will be performed for selected endpoints in subjects whom withdrawal was attempted and not attempted in order to provide supporting information to the main analyses. Demographic and baseline characteristics of patients will be summarized descriptively by treatment group, by means and standard deviations (SDs) for continuous variables and frequency distribution for categorical variables. Summaries will be performed based on the data set.

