11.3 Collection of Safety Information

An *Adverse Event (AE)* is defined as any untoward medical occurrence in a patient or clinical investigation subject administered a pharmaceutical product and that does not necessarily have to have a causal relationship with this treatment. An AE can therefore be any unfavorable and unintended sign (including an abnormal laboratory finding, for example), symptom, or disease temporally associated with the use of a investigational (medicinal) product (IP), whether or not considered related to the IP.

During clinical trials, adverse events can be spontaneously reported or elicited during open-ended questioning, examination, or evaluation of a subject. (In order to prevent reporting bias, subjects should not be questioned regarding the specific occurrence of one or more adverse events.)

Following the subject's written consent to participate in the study, all serious AEs should be collected, including those thought to be associated with clinical trial procedures. The collection of non-serious AE information should begin at initiation of investigational product. Non-serious AE information should also be collected from the start of a placebo lead-in period or other observational period intended to establish a baseline status for the subjects. Following study completion, any SAE thought to be related to study drug or clinical trial procedures should also be reported.

Certain adverse events occur commonly in this study population and will not be recorded as an adverse event, unless it is believed to be associated with the study medications (Alemtuzumab, Sirolimus, Belatacept) and/or it meets the definition of a serious adverse

event. This list is inclusive of, but not limited to events noted below, and will be at the discretion of the Principal Investigator.

Occurrence of:

- Post-op pain.
- Isolated upper respiratory infection, nasopharyngitis, cough, dyspnea and bronchitis.
- Isolated episodes of diarrhea, constipation, nausea, abdominal distention and vomiting.
- Hypokalemia/hyperkalemia, hyponatremia/hypernatremia, hypocalcemia, hypercalcemia, hypophosphatemia/hyperphosphatemia, /hypomagnesemia,/hypermagnesemia, hyperuricemia and hyperglycemia
- Peripheral edema
- Hematuria, proteinuria, glycosuria and dysuria.
- Headache, dizziness, tremor, insomnia, anxiety, fatigue and depression.
- AVF thrombosis and renal artery stenosis.

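### The AE/SAE summary by treatment group most naturally pools combination, taper and monotherapy time; no planned summary isolates serious infection, malignancy/PTLD or other SAEs after sirolimus stops

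*Combined protocol and SAP*

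**What the plan says.** The safety analysis in section 4.2 has two parts: "All AEs and SAEs will be summarized by treatment group", and laboratory values are summarized descriptively. Section 4.1 defines the safety set as "all patients who receive at least one dose of belatacept and will be used for all safety analyses". That set has no time window.

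Exposure changes within a patient. Section 3.1 gives sirolimus plus belatacept for at least a year after alemtuzumab, then a taper for eligible patients who agree, and then: "After sirolimus is discontinued, patients will remain on belatacept monotherapy indefinitely".

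Three other planned summaries touch on this:

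- The primary endpoint (section 4.2) covers 365 days on belatacept only, and counts biopsy-proven acute rejection, DSA and graft loss.
- Secondary objective 4 (section 2.2) is "Assessment of the composite of occurrence of malignancies, and opportunistic infections by 1, 3 and 5 years". The neighbouring objectives count from transplant, and this one is read the same way.
- Section 4.1 adds: "Subgroup analyses will be performed for selected endpoints in subjects whom withdrawal was attempted and not attempted". The endpoints are not named.

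**The concern.** Section 4.2 uses the same grouping phrase for baseline characteristics and for the primary proportion. Both need a grouping of patients, not of follow-up time. Whether the columns are the whole cohort, cohort 1 and cohort 2, or the first cohort's marrow randomization (section 1.3.5), a patient stays in one column throughout. A serious infection in month 3 on full combination therapy would sit beside one in month 40 on belatacept alone.

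Belatacept monotherapy is the regimen the trial aims to reach, and section 7.6 ties PTLD and PML to the overall level of immunosuppression. A reader will want to know which serious events occurred on monotherapy and which came before it. The stated table cannot show this, and the other summaries answer it only in part.

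**Working it through.** **The plan's own figures.** Section 3.4 reproduces: 20 − 0.20 × 20 − 4 = 12 attempts. Assuming that "the probability of a subject in whom withdrawal is attempted being successfully withdrawn from sirolimus for one year is 50" percent, 12 × 0.50 = 6 successes.

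**Inputs for exposure (current cohort only).**
- 20 patients (section 3.1), with five years each assumed. The synopsis says up to five years and section 3.1 at least five. Total 20 × 5 = 100 patient-years, with no death or dropout.
- Early stop of sirolimus: week 53 plus the fastest 8-week taper (section 6.2) = week 61, about month 14. Section 3.1's three-month minimum moves this to about month 15.
- Late stop: taper starting at week 104 and lasting 6 months (section 8.1, Year 1 Medication Flowchart) = month 30.
- The documents do not say how long patients who fail withdrawal stay on monotherapy.

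**Monotherapy patient-years.**
- Low: 6 successes, late stop, failures contribute nothing: 6 × (60 − 30)/12 = 15.
- High: all 12 succeed, early stop: 12 × (60 − 14)/12 = 46 (about 45 with the three-month taper).
- Middle: 6 successes plus 6 failures at one year each (assumption): late stop 6 × 2.5 + 6 = 21; early stop 6 × 46/12 + 6 = 29.

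Out of 100 patient-years, the share of a whole-cohort column that is not monotherapy runs from 100 − 46 = 54% to 100 − 15 = 85%.

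**Could the planned pieces be combined?** Weaning cannot start before week 53, so the year-1 composite is wholly pre-monotherapy. The most favourable construction is the composite between years 3 and 5 in attempted patients, which is 12 × 2 = 24 patient-years. In the middle case, successes give 6 × 2 = 12, and failures give 0 (stop at month 14) to 6 × 0.5 = 3 (stop at month 30, failure at month 42). Monotherapy is then 12/24 = 50% to 15/24 = 63%, or 100% if all 12 succeed. This requires the composite to be one of the unnamed selected endpoints, and it omits all other SAEs.

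**Likely serious-infection content, middle case.** Appendix C's SAE table gives 17 serious infections, 23.0%, which fits 74 patients on the more intensive regimen. The table's title and column heads could not be read. Mean exposure was 300 days (section 1.3.4).
- Rate: 17/(74 × 300/365.25) = 0.280 per patient-year. If the table, like its sister AE tables, runs to 56 days after the treatment period, the window is up to 356 days and the rate is 17/(74 × 356/365.25) = 0.236.
- Patients with at least one event, constant rate *r*, successes at risk for *t* years: 6(1 − e^(−rt)) + 6(1 − e^(−r)).
- *r* = 0.280: *t* = 2.5 gives 3.0 + 1.5 = 4.5; *t* = 46/12 gives 3.9 + 1.5 = 5.4.
- *r* = 0.236: 3.9 and 4.8.
- At the ends of the exposure range, with *r* = 0.280: 6(1 − e^(−0.700)) = 3.0, and 12(1 − e^(−1.073)) = 7.9.

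That rate is a first-year rate with basiliximab, MMF and steroids, so the true content is probably lower.

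**PTLD.** Section 7.6 gives 14 of 949 over 36 months. With three years each assumed, 14/(949 × 3) = 0.0049 per patient-year, so 0.07 expected cases on 15 patient-years and 0.23 on 46.

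**Precision with no events.** The exact 95% upper limit is 3.689/15 = 0.25 to 3.689/46 = 0.08 per patient-year.

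**The case against.** **The term is undefined.** The current cohort is non-randomized with one regimen, and the safety set is called as-treated. A grouping by treatment received, such as withdrawn or not, cannot be excluded. A reader might infer that the label is fixed for each patient on any interpretation; the documents do not establish that. The patient-level reading is the most natural one, given the phrase's other uses in section 4.2. Even a withdrawn/not-withdrawn split would divide patients and leave first-year events in the withdrawn column.

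**Monotherapy safety is partly covered.** This stands for rejection, DSA and graft loss in the 365-day window, and for the year-1 composite as a clean pre-monotherapy figure. It would be wrong to say the plan gives nothing on monotherapy safety. The gap is infection, malignancy and other SAEs after weaning.

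**The counts will be small and selected.** This also stands. Patients reach monotherapy by passing rejection, DSA, renal and biopsy criteria (section 6.2), so lower rates there would partly reflect selection. A late PTLD may reflect earlier depletion and combination therapy. Recurrent SAEs in a few patients are not independent, which weakens Poisson limits on all events.

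**It can be done later.** True, and no data would be lost. However, patients who fail withdrawal may go to sirolimus, CNIs, antimetabolites or steroids (section 6.2). Assigning events to regimens therefore needs rules, which are better set before results are seen.

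**Conclusion.** The point holds as a cheap improvement to a descriptive plan. On its most natural reading, the planned table pools three exposures, and no other planned summary isolates serious infection, malignancy/PTLD or other SAEs on belatacept alone.

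About 54% to 85% of a pooled column for the current cohort would not be monotherapy. This rests on 20 patients, five years each, the section 3.4 attempt and success counts, and the stop times above. It is illustrative, not a strict bound. It excludes the first cohort, whose monotherapy time could not be judged because part of section 1.3.5 was not available.

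Two tighter or larger figures are tempting and should not be used. A non-monotherapy share of 71% to 79% follows only if every failure contributes exactly one year, which no document states. A figure of 6 to 8 patients with serious infection comes from multiplying the rate by 21 to 29 patient-years. That product counts events, not patients; the same inputs give about 4 to 5 patients, and probably fewer on a lighter, later regimen. For PTLD, well under one case is expected, so only a listing is useful.

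**What to change.** Define treatment group in section 4.2, keep the overall AE/SAE summary, and add text such as:

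*SAEs, death, graft loss, malignancy, PTLD and serious infection will also be summarized by the regimen in force at onset (belatacept with sirolimus or its substitute; taper; belatacept monotherapy; other). Subjects with events, number of events and patient-years at risk will be given, with a dated per-patient listing of regimen at onset. Time at risk ends when collection of that event type ends (section 11.6). Periods will not be compared causally.*

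Rates with exact Poisson limits are optional and should use first events per patient.

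Leave non-serious AEs out of this summary because their ascertainment varies. For cohort 2 patients on stable sirolimus, not weaning and receiving commercial belatacept as outpatients, "then adverse events may be assessed every three months" instead of monthly (section 8.1). Cohort 1 follows a six-monthly and yearly schedule. Section 11.3 also says "Certain adverse events occur commonly in this study population and will not be recorded as an adverse event", with exceptions for serious or drug-related events.

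The cost is a short addition to the text and some programming. Immunosuppressive medications (section 4.1), study drug use (section 6.5) and AE onset dates (section 11.3) are already recorded. Section 11.6 requires death, graft loss, malignancy, PTLD and serious infection to be reported to study end; its reference to randomized subjects should be reworded to cover the non-randomized cohort. The downside is sparse counts in selected, later-period patients, with possible carry-over from earlier therapy, which the report should state.
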